The goal of this Fast-Track STTR project is to optimize and test a novel arm restraint in older critically ill mechanically ventilated patients that increases mobility; reduces agitation, use of sedative medications, and delirium; and exhibits high satisfaction and acceptability among hospital staff, family members, and patients. Older mechanically ventilated patients are often immobilized with wrist restraints to prevent self-extubation and are sedated to reduce agitation caused by their restraints and endotracheal (breathing) tube. This sedation and immobility lead to complications, including delirium and muscle weakness, that are independently associated with long term cognitive impairment, reduced physical functioning, and mortality. Specifically, the incidence and duration of delirium in the ICU are strongly and independently associated with long-term cognitive impairment that is similar to Alzheimer's Disease and Related Dementias.

Healthy Design is developing the novel *Exersides*TM restraint that allows arm mobility but prohibits hands from reaching oral/nasal endotracheal and feeding tubes or intravenous lines. Because it permits mobility, *Exersides*TM may reduce agitation and the need for sedatives. In preliminary pilot testing, *Exersides*TM has demonstrated very encouraging results. The objectives of this STTR Fast-Track project are to optimize *Exersides*TM and evaluate it in a randomized controlled trial (RCT) in older critically ill patients at high risk for delirium and associated long-term cognitive impairment. The multidisciplinary investigator team has expertise in critical care, extensive experience in conducting ICU RCTs, and a history of successful collaboration.

During Phase I, a prospective study will be performed in 8 older mechanically ventilated patients to demonstrate that 1) the revised *Exersides*TM prototype is safe and 2) the RCT proposed in Phase II is feasible. The milestones to proceed to Phase II are to demonstrate that: 1) the revised *Exersides*TM restraint has mean incidence rate <5% across 7 pre-specified safety criteria in mechanically ventilated

older patients who require restraint; and 2) the RCT in phase II is feasible by successfully enrolling 8 ICU patients into the phase I study and completing at least 90% of all proposed outcome measures.

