

18 Patton MQ. Qualitative Research & Evaluation Methods: Integrating Theory and Practice. 4th ed. Thousand Oaks, CA: Sage Publications, 2015;

20 Nalamalapu SR, [name] DM, [name] RD. Patient Recruitment Rate in Multicentered Randomized Trials in Critical Care. *Crit Care Med* 2016; 44:e588-589

Objectives: Clearly state the primary and secondary objective(s) of the study.

Phase I Specific Aims:

1. To revise the *ExersidesTM* prototype based on feedback obtained from standardized patients in the UVM simulation center.
2. To demonstrate that the revised *ExersidesTM* restraint is safe, and that conducting the proposed RCT (for STTR Phase II) is feasible, by performing a prospective evaluation in 8 mechanically ventilated older patients who require wrist restraint, including pilot testing all proposed measurements and outcomes planned for STTR Phase II

Milestones to progress to Phase II: (A) Demonstrate that the revised *ExersidesTM* prototype is safe in older mechanically ventilated patients who require restraint (i.e., has mean incidence <20% across pre-defined safety criteria, including: skin breakdown and laceration, reportable injuries to patients and clinicians, self-removal of the restraint, and damage to ICU bed or equipment), and (B) Demonstrate feasibility of the RCT planned for STTR Phase II, including enrollment of 8 ICU patients and completion of >90% of all outcomes/measures.

Phase II Specific Aims:

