- Description of restraint intervention:** All 8 patients will wear both the *Exersides™* and traditional wrist restraint devices on both arms, sequentially, over 2 study days. On Day 1, they will wear the *Exersides™* restraint on both arms from 9am-1pm and wrist restraints on both arms from 1pm-5pm. On Day 2, they will wear the restraints on both arms in the opposite order. During each 4-hour period, subjects will be observed by research and nursing staff, with validated and reliable hourly assessments of sedation/agitation (RASS) status,¹ and validated and reliable delirium assessment (CAM-ICU) at the start and stop of each period (see Aim 3, Outcome 2 for description of RASS and CAM).¹ Subjects will wear actigraphs on both wrists to measure mobility/activity continuously. A digital video camera will be set up at the foot of the patient's bed to continuously record his/her movements during the study sessions. Overnight between Days 1 and 2, subjects will resume traditional restraints, per MD order. Intervention ends on Day 2. Satisfaction/acceptability/perceptions of device will be assessed in nurses, family members, physicians, and patients as per RCT protocol (see Aim 3, Outcome 3).
- Phase I Outcomes:**

1. Demonstrate that revised prototype is safe, with <20% mean incidence across 7 safety criteria in the 8 subjects enrolled. Safety criteria in STTR Phase I will include: 1) clinician or patient laceration (Grade 2b or higher, per STAR laceration grading criteria⁹) from any sharp edges of device, 2) development of pressure ulcer from device of Stage 3 or greater per 2016 National Pressure Ulcer Advisory Panel Pressure Injury Stages,¹⁰ 3) reportable injury (per local institutional standards) of patient by device, 4) reportable injury (per local institutional standards) to clinician by device, 5) self-removal of device, 6) damage to hospital bed rendering it non-functional, and 7) damage to ICU equipment (e.g. ventilator) rendering it non-functional..
2. Demonstrate that conducting the proposed RCT in Aim 3 is feasible, by consent/recruitment rate and pilot testing measures/outcomes for the RCT, via the following tasks:
 - **Consent/Recruitment:** 8 patients consented and enrolled within ≤ 7 months

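### The Phase I safety milestone averages seven unlike criteria with no limit on any one of them, so under the <20% cut-off no single criterion can fail it, even if all 8 patients remove the device

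*Combined protocol and SAP*

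**What the plan says.** The safety milestone appears in three places.

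- Phase I, Aim 2, Phase I Outcomes, item 1: "Demonstrate that revised prototype is safe, with <20% mean incidence across 7 safety criteria in the 8 subjects enrolled". The seven criteria are laceration of patient or clinician, pressure ulcer of Stage 3 or greater, reportable patient injury, reportable clinician injury, and then "5) self-removal of device, 6) damage to hospital bed rendering it non-functional, and 7) damage to ICU equipment (e.g. ventilator) rendering it non-functional".
- Objectives, Milestones to progress to Phase II: safe is spelled out as a device that "has mean incidence <20% across pre-defined safety criteria", followed by a shorter, grouped list.
- Project summary, opening section: the same milestone, but the "restraint has mean incidence rate <5% across 7 pre-specified safety criteria in mechanically ventilated" patients.

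None of these gives a limit for an individual criterion, a weighting, or a rule for the worst criterion. None says whether incidence counts patients or events, or what the denominator is for clinician, bed and equipment events. Self-extubation is to be reported in Phase I but is not one of the seven criteria.

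Two reviews sit outside the milestone. Under Phase I Study follow-up, the engineer reports on all Phase I assessments and decides with project leadership which modifications are needed before the RCT. Under the Data Safety Monitoring Plan, the DSMB looks at the Phase I data before the RCT starts. Neither has a numeric criterion.

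**The concern.** The decision statistic is an average over outcomes that cannot stand in for one another. Injury to a patient, escape from the restraint, injury to a clinician, a broken bed and broken equipment each carry one seventh of the weight. A zero on bed damage offsets a failure on self-removal, and the more criteria that stay at zero, the more failure in another the rule tolerates.

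Self-removal matters most here because it is the only one of the seven that measures loss of restraint, and the device is meant to keep the hands away from tubes and lines. If that criterion can reach 100% without failing the milestone, meeting the milestone does not show that the prototype restrains. It is also the only numeric safety gate before a 54-patient RCT in which patients may wear one device for up to 4 more days after the crossover, against two 4-hour Exersides sessions in Phase I. The RCT's primary estimate is not affected; what is at stake is whether the Phase I conclusion follows from its own rule.

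**Working it through.** **Inputs.** 8 patients and 7 criteria (Aim 2); cut-off <20% (Aim 2 and Milestones) or <5% (project summary). The cut-offs are set rather than derived, and N = 8 rests on feasibility, so there is no error rate to reproduce.

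**Assumption.** Equal weights, and each criterion counted once per patient as yes or no. Then

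mean incidence = (1/7) x sum over criteria of (patients with the event / 8) = positive cells / 56.

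**Step 1: what each cut-off allows in total.**

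| Cut-off | Most positive cells that pass | First that fails |
|---|---|---|
| <20% | 11/56 = 19.6% | 12/56 = 21.4% |
| <5% | 2/56 = 3.6% | 3/56 = 5.4% |

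**Step 2: one criterion alone, the other six at zero.** The maximum is (8/8)/7 = 8/56 = 14.3%.

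- <20%: 8 of 8 passes, and 11 - 8 = 3 further events could be added. No single criterion can breach this cut-off. With 8 of 8 self-removals, the exact two-sided 95% lower limit for the true rate is 0.025^(1/8) = 63%, and the milestone is still met.
- <5%: 8 of 8 (14.3%) and 3 of 8 (5.4%) fail; 2 of 8 patients (25%) pass at 3.6%.

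**Step 3: a harm counted under two criteria.** Criterion "3) reportable injury (per local institutional standards) of patient by device" may cover the same event as the laceration or ulcer criterion.

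- <20%: 8 of 8 patients gives 16/56 = 28.6%, a fail; 5 of 8 gives 10/56 = 17.9%, a pass.
- <5%: 2 of 8 gives 4/56 = 7.1%, a fail; 1 of 8 gives 2/56 = 3.6%, a pass.

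**Step 4: other readings of the count.**

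- Events rather than patients: one self-removal in each of the two Exersides sessions for every patient gives (16/8)/7 = 28.6%, which fails <20%.
- The grouped list in the Milestones read as fewer categories, with one at 100%: four give 25% and five give 20%, both fails; six give 16.7% and seven give 14.3%, both passes. Aim 2 and the summary both say seven.

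**Step 5: a separate limit per criterion at N = 8.** 1/8 = 12.5% and 2/8 = 25%, so <20% means at most 1 of 8 and <5% means 0 of 8. Self-removal in 8 of 8 then fails at 100%.

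**The case against.** The strongest reply is that the milestone is not the only safeguard. The investigator monitors Phase I, the engineer and project leadership decide on modifications, and the DSMB sees the Phase I data and can recommend changes or a stop. A reader might infer that a device removed by all 8 patients would go into the RCT unexamined; the documents do not support that. What does not stand is that these reviews repair the rule: none has a numeric criterion, and none changes what the milestone certifies.

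Three further objections are sound and limit the point.

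- It is tempting to say that no single harm can fail the <20% version. The criteria are not stated to be mutually exclusive, so an injury counted twice can fail at 28.6%. The statement is secure for a single criterion, and self-removal without injury is the clear example.
- It is tempting to say that the rule can never detect a device that fails consistently in one way. Under the summary's <5% it does so from 3 of 8 patients.
- The documents give no data showing that bed, equipment or clinician events will be zero, or that self-removal is the likeliest failure. No self-removal was seen in the 5 pilot patients who wore Exersides. Self-removal in 8 of 8 is a stress test of the rule, not a forecast, and the 1/7 ceiling does not depend on either claim.

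**Conclusion.** The point holds in a limited form. With seven equally weighted criteria counted yes/no per patient, the <20% milestone cannot be failed by any one criterion: self-removal in every patient scores 14.3% and the prototype meets the protocol's definition of safe. A harm counted under two criteria can still pass in 5 of 8 patients. Under <5% the extreme case disappears, but a 25% rate on one non-overlapping criterion still passes.

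The size therefore depends on which cut-off applies, which the documents leave contradictory, and on a counting rule they do not state. Both gaps are further reasons to rewrite the milestone. Under either cut-off, meeting it does not show that any particular failure was uncommon.

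**What to change.** 1. Reconcile the cut-off across the project summary, the Milestones to progress to Phase II, and Aim 2, Phase I Outcomes. The choice is the sponsor's.
2. In all three places, replace the average with a requirement that each of the seven criteria separately meets that cut-off, counted as patients with at least one event out of 8. State the resulting limit (at most 1 of 8 for <20%; 0 of 8 for <5%). For clinician, bed and equipment events, say that the event is attributed to the patient in whose session it occurred.
3. Report alongside it the proportion of the 8 patients with any patient-harm or self-removal event. This should be reported, not made a pass condition: at <20% it would also stop on two unrelated events in two patients, which is a debatable tightening.

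This is a change of wording and uses data already planned. The cost is a stricter gate at N = 8. At <5%, the separate limits together amount to no event of any kind, so an assumed any-event risk per patient of 5% would fail with probability 1 - 0.95^8 = 34%, and 10% would fail with probability 1 - 0.90^8 = 57%. At <20%, a single criterion with an assumed true risk of 5% would fail with probability 1 - 0.95^8 - 8 x 0.05 x 0.95^7 = 5.7%; the risk over all seven criteria would be higher. The sponsor should weigh these figures when settling the cut-off.

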Configurations for adjustable levels of restraint are: 1) no tie for a calm patient, 2) resistance tie (intermediate level of restraint) for a patient with flailing arms OR for resistance exercise as might be supervised by a physical therapist or nurse, and 3) rigid tie for temporary tighter restraint for an agitated or aggressive patient or as a temporary restraint during a procedure when the arm must be immobilized.

2. An evaluation in healthy subjects demonstrated that the first *Exersides*TM prototype was feasible to use and comfortable for subjects. The prototype was tested in 6 registered nurse (RN)

Figure 1. *Exersides*TM restraint prototypes in use.

A: Healthy volunteer able to move arm from the shoulder but the restrained hand is unable to self-extubate or remove the device. Adjustable levels of restraint possible using resistance or rigid (white) straps. **B:** The *Exersides*TM restraint (both arms) in use by an awake patient mechanically ventilated for acute lung injury and able to participate in care.

A

B

volunteers who, following consent, were videotaped and acted in both their staff role (bedside RN) and simulated patient role (performed in a hospital bed). In the patient role, volunteers were instructed to act as: 1) a calm and cooperative patient, 2) a confused patient with moving arms, and 3) an agitated patient. Results, summarized in Table 1, demonstrate high satisfaction.

3. A pilot study of first prototype *Exersides*TM restraint in ICU patients demonstrated feasibility and potential benefit. An IRB-approved pilot study was conducted in one Vermont hospital ICU, where 10 mechanically ventilated patients were alternately assigned to wear *Exersides*TM or traditional wrist restraints (n=5 in each group, 64±7 years old, 30% women). On day #3 of intubation, all patients were continuously videotaped for 4 consecutive hours while wearing their assigned device. All 5 patients in the *Exersides*TM group tolerated the device with no adverse events (defined as no self-extubation, feeding tube or IV dislodgement, self-removal of restraint, skin breakdown or bodily trauma to patient or nurse).

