 - **Outcomes/measures:** At least 90% of all outcomes planned for the RCT in Aim 3 (STTR Phase II) will be measured in the 8 patients: 1) actigraphy counts, 2) RASS sedation/agitation score,¹ 3) CAM-ICU delirium score,¹ 4) medication use, 5) satisfaction/acceptability/perceptions of novel restraint. Incidence of self-extubation will also be reported in addition to the following measures of efficacy: 1) patient-reported satisfaction measures including comfortable, safe, effective, preferable and more humane; and 2) staff-reported satisfaction measures including easy to don/doff, easy to change level, safe for staff, effective, preferable and more humane. See Aim 3 for these RCT measures.

- **Data collection/management, quality assurance & analysis:** See Aim 3.
- **Sample size:** N=8 was based on feasible enrollment from the single study site during the 9-month Phase I period (i.e., ~1 patient/month). Literature suggests that there is no advantage to including more than 6-10 subjects per group in a Phase I study, and most chemotherapeutic phase I studies have N=3 per cohort.¹ Thus, N=8 is adequate for the proposed Aims to prepare for the RCT in Aim 3.
- **Phase I Study follow-up.** The engineer will prepare a report on the outcomes of all assessments based upon STTR Phase I, and will decide (in consultation with the project leadership team) which device improvements/modifications will be required before use of device in Aim 3 (STTR Phase II).

PHASE II (3-site RCT to compare the novel restraint to traditional wrist restraints)

[figure not shown]
Aim 3: To conduct a multi-site, within-patient randomized crossover trial in older critically ill mechanically ventilated patients who require restraint, to compare the *Exersides™* restraint vs. traditional wrist restraints.

Overview and Study Design Phase II. The objective of the Phase II project is to conduct an RCT to measure 3 outcomes:

1. Mobility/activity evaluated by actigraphy (primary outcome)
2. Agitation, delirium, medication use (sedative, analgesic, and antipsychotic), and incidence of self-extubation (secondary outcomes)
3. Satisfaction with, and acceptability/perceptions of, the device by patient, family, and clinicians (secondary outcomes)

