Safety monitoring also will occur via the PIs and co-Is being involved in the conduct of the clinical trials including supervising the screening for patient eligibility. The PIs will have knowledge of any adverse events that may arise and will report them according to IRB and NIH/NIA guidelines and to the description provided below. All potential participants will be provided contact information for the IRB of record (University of Vermont, Johns Hopkins University, University of California) to register complaints or other problems. The DSMB will modify or stop the study if any such complaints represent a legitimate concern about the study procedures or methods. The design of the proposed studies and the proposed *Exersides*TM restraint intervention are not complex and have very low potential risk to the patient. Our preliminary data demonstrate that the *Exersides*TM restraint is safe, as we experienced no adverse events in the pilot study already completed with the prototype device. The physical restraint device proposed for this trial is a Class I medical device under US Food & Drug Administration regulation 21 C.F.R. § 880.6760 subject to general controls and is exempt from Federal Drug Administration (FDA) approval. The relatively low risks will be further minimized as described in the above Human Subjects section entitled "Protection Against Risks." Confidentiality of participants' data will be protected by having all identifying participant-information removed from databases before analysis. Electronic data storage will be password protected with daily back-up and storage. Only research associates who directly interact with research subjects will have access to participant identifying information. All filing cabinets and storage facilities that contain sensitive patient information will be locked when not used. All computers and storage cabinets will be located within secure office locations.

Adverse Event and Unanticipated Problem (UAP) Reporting: Describe how events and UAPs will be evaluated and reported to the IRB. All protocols should specify that, in the absence of more stringent reporting requirements, the guidelines established in the Committees on Human Research "Adverse Event and Unanticipated Problems Reporting Policy" will be followed. The UVM/UVM Medical Center process for review of adverse events and UAPs to subjects or others should be included in the DSMP.

1. *Events of Interest*

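### Phase I sets out to demonstrate safety from an observed mean in 8 patients with no confidence bound, which the design cannot do

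*Combined protocol and SAP*

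**What the plan says.** Aim 2 is framed as demonstrating the safety of the restraint. Item 1 of its Phase I Outcomes gives the rule: "Demonstrate that revised prototype is safe, with <20% mean incidence across 7 safety criteria in the 8 subjects enrolled". The milestone for moving to Phase II, under the Phase I Specific Aims, uses the same limit ("has mean incidence <20% across pre-defined safety criteria"). The project summary at the front of the protocol gives a different one: "restraint has mean incidence rate <5% across 7 pre-specified safety criteria in mechanically ventilated".

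The Aim 2 sample-size paragraph says "N=8 was based on feasible enrollment from the single study site during the 9-month Phase I period (i.e., ~1 patient/month") and concludes: "Thus, N=8 is adequate for the proposed Aims to prepare for the RCT in Aim 3". For analysis, Aim 2 points elsewhere: "Data collection/management, quality assurance & analysis: See Aim 3". The Aim 3 Statistical Analysis Plan has no interval, test or error rate for the seven safety criteria.

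The pilot is a separate matter. Preliminary Studies, item 3, reports that "All 5 patients in the" device group tolerated the first prototype with no adverse events during a 4-hour observation. The Data Safety Monitoring Plan treats the restraint as shown to be safe, "as we experienced no adverse events in the pilot study already completed with the prototype device". The Potential Risks section and the device risk assessment make the same claim from the same data.

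**The concern.** Demonstrating that an incidence lies below a limit means excluding, with stated confidence, that it lies at or above the limit. The Phase I rule asks only that the observed value fall below it. With 8 patients the two can differ widely, and the plan gives the reader no means of seeing by how much.

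Passing is a milestone for opening a 54-patient RCT in which device exposure rises from two 4-hour sessions to as much as four further days. The pilot statements feed the description of risk to subjects and the non-significant-risk assessment, in a trial where most consent comes from surrogates. In both places the strength of the evidence should be stated as it is.

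**Working it through.** **Inputs.** 8 patients and 7 criteria (Aim 2, Phase I Outcomes, item 1); limits of 20% (that item and the milestone) and 5% (project summary); pilot 0 of 5 patients, 4 hours each (Preliminary Studies, item 3). The plan states no error rate or bound for the rule, so there is no figure to reproduce.

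**Assumptions.** Each criterion is scored yes or no once per patient. The documents give no true incidence and no dependence between cells. The base case is independent cells. The range uses a beta-binomial model by patient with within-patient correlation 0.1 and 0.3. Limits are exact, one-sided 95%.

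**1. What passes.** Cells: 8 × 7 = 56. For 20%: 0.20 × 56 = 11.2, so 11 or fewer events pass (11/56 = 19.6%). For 5%: 0.05 × 56 = 2.8, so 2 or fewer pass.

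**2. What a pass under the 20% rule excludes.** The upper limit solves P(Bin(56, p) ≤ 11) = 0.05, giving p = 30.4%. With within-patient correlation it is about 33% (0.1) or 38% (0.3).

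**3. Probability of passing the 20% rule**, P(Bin(56, p) ≤ 11):

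| True mean | Independent cells |
|---|---|
| 10% | 99% |
| 20% | 55% |
| 25% | 22% |
| 30% | 5.7% |

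At correlation 0.3 the figures are 55% at a true 20% and 34% at a true 25%.

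**4. The 5% limit.** With no events at all, the upper limit is 1 − 0.05^(1/56) = 5.2%, already above 5%. Positive within-patient correlation widens it. For 2/56, the worst result that passes, it is 10.8%. A device at a true 5% passes 46% of the time.

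**5. One criterion.** For 0/8 the upper limit is 1 − 0.05^(1/8) = 31.2%. A harm affecting 10% of patients goes unseen in all 8 with probability 0.9^8 = 43%.

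**6. Pilot.** For 0/5 the upper limit is 1 − 0.05^(1/5) = 45.1%. If 20% of patients were affected, a clean pilot would still occur with probability 0.8^5 = 33%.

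**7. Would a gate on the pooled upper limit solve it?** With independent cells the upper limit is 17.9% for 5/56 and 20.1% for 6/56, so a gate requiring a limit below 20% would allow 5 events. The gate depends on independence:

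| Within-patient correlation | Upper limit, 5/56 | True 20% device passes |
|---|---|---|
| 0 | 17.9% | 2.1% |
| 0.1 | 20.3% | 5.5% |
| 0.3 | 24.6% | 12.4% |

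Self-removal in 5 of 8 patients with no other event gives 5/56 = 8.9% and would pass. With independent cells, a device at a true 10% would fail about half the time (it passes with probability 51%).

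**The case against.** Phase I is described as a small study of feasibility and safety, and N=8 is openly based on achievable enrolment. The adequacy sentence is qualified as preparation for the RCT. The milestone is also not the only safeguard. The engineer and project leadership decide on device changes after Phase I. The DSMB reviews the Phase I data before the RCT, can recommend stopping, and meets again at 27 patients. All of this stands and keeps the point from being more serious. It does not supply the missing bound, and nothing requires that these reviewers be given one.

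Any rule that compares a point estimate with a limit passes about half the time when the truth sits at that limit, so the 55% is no special flaw of this rule. That is correct. It shows that such a rule can guide a decision but cannot demonstrate incidence below the limit.

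Three stronger readings are tempting and not supported:

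- A reader might apply the 20% limit and the 55% to the pilot as well. The pilot has no limit and no pass rule; its weakness is the 45% upper limit.
- A reader might infer that the low-risk statements rest on passing Phase I. They cite the completed pilot, the device design and, in the Data Safety Monitoring Plan, Class I device status.
- A reader might say the pilot is taken as proof. The protocol discloses the 5 patients and 4 hours, names residual risks and promises expanded safety data from Phase I. What is unsupported is the wording that the pilot demonstrates safety.

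**Conclusion.** The point holds as a mismatch between what Phase I claims and what 8 patients can show. Under the 20% rule a passing result is compatible with a true mean of 30.4% in the favourable case of independent cells, and of about 33% to 38% under the assumed correlations. Under the 5% limit no possible result demonstrates the claim. The 5% and 20% statements contradict each other and must be reconciled; the conclusion is the same under either. The pilot claim is a separate matter of wording, with an upper limit of 45% for 4-hour use of an earlier prototype.

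The correlations are assumptions, because the documents give none. The single-criterion and pilot limits do not depend on them. They assume only that patients are independent and share a common risk.

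**What to change.** - **Milestone and Phase I Outcomes, item 1:** keep a go/no-go on observed incidence, call it descriptive, and do not describe passing it as demonstrating safety. Reconcile the 5% and 20% limits across the project summary, the milestone and the outcome.
- **Phase I analysis:** report each of the seven criteria as patients affected out of 8 with an exact one-sided 95% upper limit. Give these limits to the engineer, project leadership and DSMB before the RCT.
- **Aim 2 sample size:** state what N=8 can exclude. With no events on a criterion, only rates above 31% are excluded.
- **Potential Risks, Data Safety Monitoring Plan and device risk assessment:** replace the claim that the pilot demonstrates safety with the result itself: 0 of 5 patients, 4 hours each, one-sided 95% upper limit 45%.
- **Do not substitute a gate of 5 events in 56.** It loses its 95% bound under clustering, can still pass a device that 5 of 8 patients remove, and rejects a true 10% device about half the time.

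The cost is wording and a few exact-binomial calculations, with no additional patients. The downside is that the stated safety claims become less favourable.

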Data Safety and Monitoring: The specific design of a Data and Safety Monitoring Plan (DSMP) for a protocol may vary extensively depending on the potential risks, size, and complexity of the research study. For a minimal risk study, a DSMP could be as simple as a description of the Principal Investigator's plan for monitoring the data and performance of safety reviews or it could be as complex as the initiation of an external, independent Data Safety and Monitoring Board (DSMB). The UVM/UVM Medical Center process for review of adverse events should be included in the DSMP.

DATA SAFETY MONITORING PLAN

The STTR Phase I Cohort Study will be monitored locally by the Principle Investigator who will assess participant safety, efficacy of the study intervention, benefit/risk, recruitment of participants, adequacy of measured and collected data, and adherence to the protocol. At the conclusion of the Phase I cohort study, we will convene a Data and Safety Monitoring Board (DSMB) that will oversee the RCT in STTR Phase II. Below, we outline the responsibilities, membership, and organization of the DSMB:

1. Responsibility: As per NIH policy, the responsibility of the DSMB will be to advise and make recommendations regarding participant safety; efficacy of the study intervention; benefit/risk ratio of procedures and participant burden; selection, retention, and recruitment of participants; adherence to protocol requirements; data and statistical analysis plan; adequacy of measured and collected data; and possible amendments to the study protocol and consent forms. As this proposal includes a small clinical trial, the main charge of the DSMB will to focus on safety, and there will be no stopping rules for efficacy or futility.

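### The Phase I safety threshold for starting the RCT is below 5% in one place and below 20% in two others, so the same data can pass and fail

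*Combined protocol and SAP*

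**What the plan says.** Three places state the safety condition that Phase I must meet.

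- **Project summary (opening section).** After the words "The milestones to proceed to Phase II are to demonstrate that", the first condition is that the revised device "has mean incidence rate <5% across 7 pre-specified safety criteria".
- **Objectives, Phase I Specific Aims.** Under "Milestones to progress to Phase II", item (A) treats the revised prototype as safe if it "has mean incidence <20% across pre-defined safety criteria".
- **Methods, Aim 2, Phase I Outcomes, item 1.** The prototype is to be shown safe "with <20% mean incidence across 7 safety criteria in the 8 subjects enrolled". The seven criteria follow: laceration of clinician or patient, pressure ulcer, reportable injury to the patient, reportable injury to a clinician, self-removal, damage to the bed, and damage to ICU equipment.

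The plan derives neither percentage. The Phase I size of 8 is justified by feasible enrolment. Mean incidence is not defined further.

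**The concern.** The three statements concern the same prototype, the same 8 patients and the same decision. The criteria also match: the list in the Objectives is shorthand for the seven items in Aim 2. This is therefore one milestone with two limits, a factor of four apart, and not two measures that happen to differ.

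It is the only numerical safety condition between Phase I and the RCT. If the result falls between the limits, whoever applies the rule can reach either answer, and would do so after seeing the data. A go/no-go rule with that property is not pre-specified. The population is older ventilated patients, most of whom are expected to lack capacity to consent.

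A smaller gap adds to this. The wording most naturally means patients with an event on each criterion, but it does not say so, and clinician injury and equipment damage are not patient events. It is also unclear whether one event may count twice. A laceration or ulcer could also be a "reportable injury (per local institutional standards) of patient by device".

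**Working it through.** **Inputs.** From the plan: 8 patients, 7 criteria, limits of <5% and <20%. Assumed, because the plan does not define it: each criterion is scored yes or no once per patient, giving 8 × 7 = 56 cells, and mean incidence = events / 56.

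**Step 1: events allowed by each limit.**

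| Limit | Largest total that passes | Next total, which fails |
|---|---|---|
| <5% | 2/56 = 3.6% | 3/56 = 5.4% |
| <20% | 11/56 = 19.6% | 12/56 = 21.4% |

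Totals of 0 to 2 pass both versions and totals of 12 or more fail both. Totals of 3 to 11 fail the first and pass the second.

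**Step 2: another denominator.** Each patient wears the novel device in two 4-hour sessions, one on each day. Scoring per session gives 16 × 7 = 112 cells. The limits become 5 events (4.5%) and 22 events (19.6%), and totals of 6 to 22 are in conflict. Three patients who each remove the device once then give 3/112 = 2.7%, which passes both versions. The counting rule moves the range of conflict but does not remove it.

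**Step 3: how often the two versions would disagree.** With 56 independent cells and a common event rate p, the probability is P(3 ≤ X ≤ 11) with X ~ Binomial(56, p). The last column allows events to cluster within patients: a beta-binomial over each patient's 7 cells, intraclass correlation 0.1 to 0.3, 400,000 simulations.

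| Assumed p | Independent cells | Correlated within patient |
|---|---|---|
| 0.5% | 0.3% | not run |
| 1% | 2% | 5–8% |
| 2% | 10% | 14–17% |
| 3% | 24% | 25–26% |
| 5% | 54% | 43–49% |
| 10% | 92% | 70–84% |

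The plan gives no cell rates, so these are assumptions and not forecasts. For scale, under independence the chance that a patient has any event is 1 − (1 − p)^7: 6.8% at p = 1% and 30% at p = 5%. With clustering it is lower, about 17% to 24% at p = 5%.

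The pilot in the Preliminary Studies does not settle the rate. It saw no events in 5 patients, with an earlier prototype and a different event list. The one-sided 95% upper bound is 1 − 0.05^(1/5) = 45% of patients.

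**Step 4: effect of scoring one event twice.** Suppose each laceration also counts as a reportable patient injury. Two patients with one laceration each give 2/56 = 3.6% scored once, which meets <5%, or 4/56 = 7.1% scored twice, which does not. Six such patients give 6/56 = 10.7% or 12/56 = 21.4%, on either side of 20%.

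**The case against.** The strongest reply is that the gate is not mechanical. The principal investigator monitors safety during Phase I: "The STTR Phase I Cohort Study will be monitored locally by the Principle Investigator who will assess participant safety". Staff observe each 4-hour period and events of interest are collected daily. The engineer, with project leadership, decides "which device improvements/modifications will be required before use of device in Aim 3". The DSMB reviews Phase I data before the RCT and may recommend changes or a stop for safety. These safeguards are real and reduce the chance that an unsafe device goes forward. None sets a numerical limit or says which threshold applies, and a DSMB reading the whole protocol would meet both figures.

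A second reply is that the summary is only a summary, and that staff would work from Aim 2, which agrees with the Objectives. That is probably how it would go in practice. But the summary expressly calls its figure a milestone, and the plan gives no order of precedence.

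Third, events may be rare. Exposure to the device is two 4-hour sessions per patient, and several criteria have a high bar, such as a Stage 3 ulcer or a bed made non-functional. At cell rates of 0.5% to 1% with independent cells, the versions would disagree only 0.3% to 2% of the time. This stands as a limit on the likely consequence. It does not make the text consistent.

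Finally, the event counts depend on the 56-cell reading. That is correct, and the 112-cell version is shown for that reason. The gap between the two percentages does not depend on the denominator.

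**Conclusion.** The contradiction stands and must be corrected. One go/no-go milestone has two limits, <5% and <20%, in current text with no rule of precedence. Any mean incidence from 5% up to, but not including, 20% gives opposite answers, whatever the denominator. Scored once per patient and criterion, that is 3 to 11 events; scored per session, 6 to 22.

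How often this would matter depends on event rates that the plan does not give: seldom if events are very rare, and about half the time at 5% per cell. The consequence is confined to the Phase I gate. The RCT's estimate and analysis are untouched.

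**What to change.** Bring the project summary, the Objectives and Aim 2 (Phase I Outcomes, item 1) to one threshold, chosen by the sponsor before Phase I data are seen. In the same sentence, state the unit of counting (per patient, if that is meant), how clinician injury and equipment damage enter the denominator, and whether one event may score under two criteria. This review does not say which threshold is right.

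The cost is an edit to three places, with no new patients or data. The choice behind the edit is a substantive safety decision and should be recorded as one.

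One note for the sponsor, which is not an error. Averaging over seven criteria can hide a failure on one of them: self-removal in all 8 patients and nothing else gives 8/56 = 14.3%, which passes the 20% version. Whether to add a limit per criterion is a separate, optional decision. It would make the gate harder to pass and is not needed for this correction.
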